7.1.2.4. Pre-Infusion Eligibility Confirmation

Subject eligibility must be reconfirmed between study Days -10 and -4 to confirm that it is safe and appropriate that the subject receives study drug.

If any of the eligibility criteria are not met the subject must not be dosed with SBT777101. In this case, the subject remains enrolled but will need to be reassessed according to the pre-infusion eligibility criteria before dosing. Subjects can be reassessed for up to 6 months after enrollment. A subject that is not dosed within 6 months of being enrolled will be withdrawn from the study. A second apheresis is not required for subjects who qualify for infusion upon reassessment and have an available SBT777101 cell product that met the release criteria.

Subjects with active infections during the pre-treatment period should not be dosed until at least four weeks after completion of IV antibiotics and two weeks after completion of treatment with oral antibiotics/anti-infectives.

7.1.3. SBT777101 Administration

Subjects will receive SBT777101 by IV infusion on study Day 1.

Subjects will be closely monitored for acute safety events at the site under direct supervision of medical staff post administration of study drug. See Section 8.1 for details of safety monitoring requirements.

7.1.4. Safety Follow-Up

Subjects will attend study visits up to Week 48 and complete study assessments as described in the protocol.

7.1.5. Unscheduled Evaluations

The subject may be requested to come to the site for an unscheduled visit if the Investigator determines that a subject needs to be evaluated at a time other than the protocol specified visits.

Results from any unscheduled assessments, including laboratory assessments, should be captured in the appropriate eCRF.

7.1.6. End of Study Visit

An end of study visit will take place at Week 48.

If a subject withdraws from the study prior to Week 48, an end of study visit will be scheduled as soon as possible, and the assessments listed for the end of study visit will be performed. The reason for early withdrawal will be captured in the eCRF.

Following completion of the end of study visits, subjects should be encouraged to enroll in a long-term follow-up study under a separate protocol for further safety evaluation.

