7.2.6.2. Replication Competent Lentivirus

Blood samples will be collected to monitor for replication competent lentivirus (RCL) per FDA guidance (FDA, 2020) using VSV-G qPCR.

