7.4.1.1. Data Collected for Subjects Withdrawn from the Study

If a subject chooses to withdraw from the study after enrollment but prior to study Day 1, SBT777101 will not be administered. All subjects that are dosed with SBT777101 and withdraw from the study will be encouraged to enroll in the long term follow-up study at the time of withdrawal.

The date and reason for study withdrawal, if available, must be recorded in the subject's eCRF. An Early Termination (ET) visit (see Appendix B) will be conducted unless consent to do so is withdrawn.

- If a subject withdraws from the study, he/she may request destruction of any samples taken and not tested to prevent future testing. The Investigator must document this in the site study records.
- Any data already generated from samples collected up to the point of withdrawal of consent will not be removed from the study database.

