APPENDIX B. SCHEDULE OF ASSESSMENTS: BASELINE AND SAFETY FOLLOW-UP PERIOD

	Safety Follow Up														UV	\mathbf{E}	
Study Week Study Day (visit window)	1					2	3 4		6 8		10	12	24	36	48/ES		T
	1	2	4 or 5	7 ±1	11 ±1	14 ±2	21 ±2	28 ±2	42 ±2	56 ±2	70 ±2	84 ±3	168 ±7	252 ±7	336 ±7		
Procedure		•		•				•	•				•	•			
SBT777101 administration	•																
Overnight stay/acute safety monitoring	•																
Patient self-temperature monitoring	•	•	•	•	•	•	•	•	•	•	•	•	•	•	•	•	•
Patient check-in (phone call, text etc) ^a		•	•	•													
Vital signs ^b	•	•	•	•	•	•	•	•	•	•	•	•	•	•	•	•	•
Adverse events ^c	•	•	•	•	•	•	•	•	•	•	•	•	•	•	•	•	•
Prior/Concomitant medications	•	•	•	•	•	•	•	•	•	•	•	•	•	•	•	•	•
Full physical exam				•				•		•					•		•
Directed physical exam	•	•	•		•	•	•		•		•	•	•	•		•	
Weight										•					•		•
12-lead triplicate ECG				•		•									•	•	•
Synovial biopsy for tissue								● ^{d,e}									•
Synovial fluid collection								●d,e				●d,e,f					•
Assessment of synovitis (clinical and/or ultrasound)								•				•					•
Urine pregnancy test	•											•	•		•		•
Lipid tests ^g															•		
Coagulation ^g													•		•		
Hematology ^g		•	•	•	•	•	•	•	•	•	•	•	•	•	•	•	•
Clinical chemistry ^g		•	•	•	•	•	•	•	•	•	•	•	•	•	•	•	•
Urinalysis ^g										•				•	•		•
Markers of inflammation h																•	
CRP		•		•		•	•	•	•	•	•	•	•	•	•	•	•
Joint count assessment (28 SJC/28 TJC)						•		•		•			•		•		•
Joint count assessment (66 SJC/68 TJC)												•					
Physician VAS						•		•		•		•	•		•		•
Subject VAS (global and assessment of pain)						•		•		•		•	•		•		•
HAQ-DI						•		•		•		•	•		•		•
FACIT-F													•		•		•
Blood samples for PK (ddPCR) i		•	•	•	•	•	•	•	•	•	•	•	•	•	•	•	•
Blood sample for cellular immunogenicity												•			•	•	•

FINAL Confidential

Version 1.0, 18-MAY-2022 Page 72 of 92

		Safety Follow Up				UV	ET										
Study Week			1			2	3	4	6	8	10	12	24	36	48/ES		
Study Day (visit window)	1	2	1 0 7 5	7	11	14	21	28	42	56	70	84	168	252	336		
	1	Z	4 or 5	±1	±1	±2	±2	±2	±2	±2	±2	±3	±7	±7	±7		
Procedure																	
Blood sample for ADA										•					•	•	•
Blood sample for exploratory inflammatory markers		•		•		•	•	•	•	•	•	•	•	•	•	•	•
Blood sample for ACPA/RF						•	•	•	•	•	•	•	•	•	•		•
Blood sample for VICM				•		•	•	•	•	•	•	•	•	•	•		•
Blood samples for exploratory biomarkers		•	•	•	•	•	•	•	•	•	•	•	•	•	•	•	•
Blood samples for RCL												•	•		•		

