ACPA = anti-citrullinated protein antibody; ADA = anti-drug antibody; CRP = C-reactive protein; ddPCR = droplet digital polymerase chain reaction; ECG = electrocardiogram; ES = End of Study; ET = early termination; FACIT-F = Functional Assessment of Chronic Illness Therapy – Fatigue; HAQ-DI = health assessment questionnaire disability index; PK = pharmacokinetic; RCL = replication competent lentivirus; RF = rheumatoid factor; SJC = swollen joint count; TJC = tender joint count; UV = unscheduled visit; VAS= visual analogue score VICM = citrullinated and MMP degraded vimentin fragment

Note: On Day 1, all assessments should be performed prior to dosing, unless otherwise specified.

- ^a Subjects should be contacted daily by the site (e.g by phone or text) following discharge through Day 7.
- ^b Vital signs must be measured approximately 15 minutes prior to infusion, then approximately every 15 minutes during the infusion.
- ^c After informed consent has been obtained but prior to initiation of study drug, only SAEs caused by a protocol-mandated intervention should be reported. After initiation of study drug, all AEs will be reported until the end of the study. After this period, the Sponsor should be notified if the investigator becomes aware of any SAE that is believed to be related to prior study drug treatment
- ^d The synovial biopsy/fluid collection can be performed at or up to 1 week after the scheduled assessment visit.
- ^e The timing of the synovial biopsy and/or synovial fluid collection in may be changed based on evaluation of data from the first dose escalation cohort.
- $^{\rm f}$ The synovial biopsy sample/fluid collection at Week 12 and at the ET visit is optional.
- g Tests included in laboratory assessments are described in protocol Appendix C.
- ^h A sample to test for markers of inflammation should be collected within 30 minutes of the onset of a suspected adverse event of infection or CRS.
- ⁱ The PK sample collected on study Day 2 should be collected at approximately the same time of day that the infusion of study drug took place on study Day 1 (+/- 1 hour). An unscheduled PK sample should be collected within 30 minutes of a suspected infusion related reaction adverse event.

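### Sections 7.1.6 and 7.4.1.1 give different assessment lists for the same early-withdrawal visit, so a dosed subject who leaves before Week 12 may have no post-dose test for replication competent lentivirus

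*Protocol*

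**What the plan says.** Two sections govern the last visit of a subject who leaves early.

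- Section 7.1.6 (End of Study Visit), on withdrawal before Week 48: "the assessments listed for the end of study visit will be performed". In Appendix B that list is the column headed 48/ES.
- Section 7.4.1.1 (Data Collected for Subjects Withdrawn from the Study): "An Early Termination (ET) visit (see Appendix B) will be conducted unless consent to do so is withdrawn".

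Appendix B treats these as two visits. Its abbreviation line reads "ES = End of Study; ET = early termination", and each has its own column.

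On vector safety, Section 7.2.6.2 states: "Blood samples will be collected to monitor for replication competent lentivirus (RCL) per FDA guidance". The sampling times are in the row "Blood samples for RCL" of the two schedules: once before dosing (Day -10 to -4, Appendix A), then Weeks 12, 24 and 48/ES (Appendix B). The unscheduled-visit and ET cells of that row are blank.

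On synovial sampling, footnote f of Appendix B says: "The synovial biopsy sample/fluid collection at Week 12 and at the ET visit is optional".

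After withdrawal, Section 7.4.1.1 adds that dosed subjects who "withdraw from the study will be encouraged to enroll in the long term follow-up study at the time of withdrawal". That study has its own protocol, which is not among the documents.

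**The concern.** A site closing out an early withdrawal has two instructions and no rule of precedence. Section 7 makes adherence to the schedule of assessments mandatory, and a coordinator or an eCRF build would naturally turn to the column labelled ET. That column lacks the RCL sample.

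This is the first human study of a lentivirally transduced product, and safety is its primary objective. Once a subject has left, the sample may not be obtainable. Coagulation and lipids are also affected. Both are in Table 4 of Appendix C as protocol-required safety tests, and change from baseline in clinical laboratory tests is part of the primary endpoint (Section 9.4.1). Whether these results exist for a withdrawn subject should not depend on which section a site happened to read.

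**Working it through.** The protocol states no figure to reproduce. The check compares the two columns of Appendix B and then counts samples.

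**Step 1: are the columns readable?** Appendix B has 17 visit columns: 15 from Day 1 to Day 336 (48/ES), then unscheduled (UV) and ET. The 30 assessment rows compared each split into exactly 17 cells, so the marks can be assigned to visits by position.

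**Step 2: where do 48/ES and ET differ?** In six rows, three each way.

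| Row | 48/ES | ET | Other post-dose marks |
|---|---|---|---|
| RCL | yes | no | Weeks 12, 24 |
| Coagulation | yes | no | Week 24 |
| Lipids | yes | no | none |
| Synovial biopsy | no | yes (optional) | Week 4 |
| Synovial fluid | no | yes (optional) | Weeks 4, 12 |
| Synovitis assessment | no | yes | Weeks 4, 12 |

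**Step 3: scheduled post-dose samples for a withdrawn subject who attends the last visit.** The count is the scheduled visits already passed, plus 1 if the list used at the last visit includes the test.

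| Test | Withdrawal | ET column | 48/ES list (7.1.6) |
|---|---|---|---|
| RCL | before Week 12 | 0 + 0 = 0 | 0 + 1 = 1 |
| RCL | between Weeks 12 and 24 | 1 + 0 = 1 | 1 + 1 = 2 |
| RCL | between Weeks 24 and 48 | 2 + 0 = 2 | 2 + 1 = 3 |
| Coagulation | before Week 24 | 0 + 0 = 0 | 0 + 1 = 1 |
| Coagulation | between Weeks 24 and 48 | 1 + 0 = 1 | 1 + 1 = 2 |
| Lipids | before Week 48 | 0 + 0 = 0 | 0 + 1 = 1 |

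The two lists differ by exactly one sample per test in every row. The rest of the shortfall against the full schedule comes from leaving early and would occur under either list.

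**Step 4: does anything else guarantee the sample?** No. RCL, coagulation and lipids are blank in the UV column. Section 7 and Section 7.2.6.1 allow extra samples for safety reasons or at the investigator's discretion, but do not require them. Long-term follow-up is encouraged only.

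**The case against.** The strongest reply is that Section 7.1.6 already does the right thing: it requires the end-of-study list, and that list includes RCL. This stands as far as it goes. A reader might infer that a dosed subject leaving before Week 12 necessarily has no post-dose RCL test. The documents do not support that, because a site following 7.1.6 would take one. What remains is that 7.4.1.1 gives the same subject a different list.

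A reader might also turn the loss into a share of a dose level: one subject in a cohort of 3 to 6 is 1/6 to 1/3, or 17% to 33%. That is not a fair size for this defect. It presupposes a withdrawal and a site that follows the ET column. Section 7.4.3 replaces escalation subjects who are lost, or who withdraw for reasons other than toxicity, before Day 28. Section 3.1.1 allows up to six further backfill subjects per dose level. Replacement does not recover the withdrawn subject's own sample, and backfill subjects are not themselves replaced, but the percentage does not describe the loss.

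Nor do the documents show that final-visit data would become non-comparable across sites. Synovial biopsy and fluid at ET are optional, so their presence would vary even with one list.

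Three further points stand. RCL is neither a listed endpoint nor in Table 4. Safety analysis is descriptive (Section 9.7). Whether an RCL sample before Week 12 is required depends on the FDA guidance cited in 7.2.6.2, which is not at hand.

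**Conclusion.** The contradiction is real and is not an artefact of the table's layout: one event, two lists, six differing rows, no precedence rule. A dosed subject who withdraws before Week 12 may have no post-dose RCL test under this protocol, depending on which list the site follows. On the same condition, there may be no scheduled post-dose coagulation result before Week 24 and no lipid result before Week 48.

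The size is at most one RCL, one coagulation and one lipid sample per withdrawn subject, and nothing where 7.1.6 is followed. This assumes that the subject attends the last visit, since someone lost to follow-up or refusing the visit has no sample under either list. It also assumes that no discretionary sample is taken and that long-term follow-up does not supply one.

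The defect does not affect DLT assessment or dose escalation. It should be fixed because the correction is cheap and the sample may not be recoverable later, but it does not threaten the validity of the study.

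**What to change.** Make Sections 7.1.6 and 7.4.1.1 and the 48/ES and ET columns of Appendix B yield one list for dosed subjects who withdraw early:

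1. In Appendix B, mark RCL, coagulation and lipid tests in the ET column for dosed subjects. Section 7.1.6 already requires these at early withdrawal, so this carries existing intent into the grid.
2. In Section 7.1.6, have the early-withdrawal sentence refer to the ET column of Appendix B, matching 7.4.1.1.
3. Leave synovial biopsy and fluid at ET optional, as in footnote f.

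The first two edits must be made together. Redirecting 7.1.6 to the ET column as it now stands would make the RCL gap definite. Pointing 7.4.1.1 to the 48/ES list instead would also secure the RCL sample, but would drop the synovial assessments now marked at ET.

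The cost is amendment wording, a matching eCRF change and a few extra blood tubes at a visit where blood is already drawn. No visit or invasive procedure is added.

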7.2. Study Assessments

Planned timepoints for all study assessments are provided in the Schedule of Assessments (SoA) (see Appendix A and Appendix B).

The preferred order of assessments is presented in Section 7.3.

7.2.1. Demographics

Data collected will include but is not limited to age (date of birth), gender, and self-reported race/ethnicity (see Section 9.6).

7.2.2. Medical History

Medical history will include but is not limited to clinically significant diseases, surgeries, cancer history (including prior cancer therapies and procedures), inflammatory/autoimmune disease, smoking history, use of alcohol and drugs of abuse within the previous year. Medical conditions that are a result of side effects from concomitant medications should be clearly defined and entered into the eCRF.

Any medical condition present at study Day 1 should be followed during the study and a change in status (intensity or frequency) should be reported as an adverse event if deemed clinically significant by the Principal Investigator.

7.2.3. Concomitant Medications

All standard concomitant medications (e.g., prescription drugs, over-the-counter drugs, herbal/homeopathic remedies, nutritional supplements) used by the subject within 30 days prior to the Screening visit should be entered on the Concomitant Medications eCRF.

Prior and current therapies used by a subject for the treatment of RA must be reported from the time of diagnosis through to the end of the study/early termination visit, where available. This includes DMARDs and corticosteroids.

A start date should be entered for all medication items entered into the Concomitant Medications eCRF, including those medications used chronically.

7.2.4. Safety Assessments

7.2.4.1. Physical Examinations

A complete physical examination or a symptom directed physical examinations will be performed.

- A complete physical examination will include, at a minimum, assessments of the
 cardiovascular, respiratory, gastrointestinal, and neurological systems. A
 genitourinary or breast examination is not required unless clinically indicated, in the
 opinion of the Investigator assessing the subject. Height and weight will also be
 measured and recorded.
- A symptom directed physical examination will include those organs, body sites required to assess the symptoms and associated findings.

7.2.4.2. Electrocardiograms

Triplicate 12-lead electrocardiograms (ECGs) will be obtained at specific timepoints during the study.

- ECGs should be performed after the subject has been at rest for at least five minutes, and whilst in a supine position.
- At a minimum, the following ECG parameters will be collected in the eCRF: HR, PR-interval, RR interval, QTc, QTcF, QRS width.
- The three ECG recordings should be performed within a five-minute period and at least 1 minute apart. If any abnormal findings are measured, then the ECGs will be repeated in triplicate (within five minutes; at least one minute apart).

7.2.4.3. Vital Signs

Vital sign assessments will be performed at specific timepoints during the study.

• Will include oral body temperature, systolic and diastolic blood pressure, and pulse and respiratory rate. Height and weight will be recorded at screening only.

- Blood pressure and heart rate measurements will be assessed after the subject has been rested for at least 5 minutes, in a quiet setting if possible, and in a supine or semi-reclined position.
- Oxygen saturation will be measured at screening, during apheresis and during infusion of study drug.

7.2.4.4. Chest X-Ray

A standard posterior-anterior and lateral chest x-ray will be obtained. All clinically significant abnormalities noted prior to SBT777101 administration should be noted on the medical history eCRF.

7.2.5. Synovial Tissue and Fluid

All subjects will undergo collection of synovial tissue and fluid pre- and post-dose for evaluation of CAR-antigen reactivity, and characterization of local inflammatory microenvironment, including the number and phenotype of T cell and other immune cell subtypes.

The presence of SBT777101 will be evaluated in the synovial fluid and tissue (if sampling is clinically feasible). Synovial biopsy should be performed in the same joint pre- and post-dose where possible.

Sites using ultrasound evaluation of joints (e.g., knees, wrists and ankles) as part of the synovial biopsy/synovial fluid collection procedure will collect ultrasound images to assess pathophysiological changes following dosing with SBT777101.

Details of procedure requirements and sample processing are provided in the Biopsy Manual.

7.2.6. Laboratory Assessments

For sampling procedures, storage conditions, and shipment instructions, see the Laboratory Manual.

7.2.6.1. Clinical Laboratory Tests

The Investigator must review the laboratory report, document this review, and record any clinically significant changes occurring during the study as an AE. The laboratory reports must be filed with the source documents.

Additional laboratory tests may be performed at the Investigator's discretion for the purpose of planning treatment administration, following AEs, or as clinically indicated.

For all females, a serum pregnancy test will be performed at the Screening and Pre-Infusion visits. Urine pregnancy tests will be done at all other study visits.

Details of laboratory tests are described in Appendix C.

7.2.6.2. Replication Competent Lentivirus

Blood samples will be collected to monitor for replication competent lentivirus (RCL) per FDA guidance (FDA, 2020) using VSV-G qPCR.

7.2.6.3. PK and Immunogenicity Assessments

Whole blood and serum samples will be collected to evaluate the pharmacokinetics and immunogenicity of SBT777101. This will include:

- Whole blood samples for PK analysis
- Serum samples for immunogenicity analysis will be collected to measure ADAs against the extracellular domain of the CAR and the EGFR tag.
- PBMCs will be collected to measure cellular immunogenicity against CAR-derived and EGFR tag-derived peptides.

In addition, the Sponsor may collect synovial tissue and fluid for analysis of presence of SBT777101.

The Sponsor may store samples for up to 15 years after the end of the study to achieve study objectives.

7.2.6.4. Pharmacodynamic and Biomarker Assessments

Whole blood and serum samples as well as synovial tissue and fluid will be collected to evaluate the pharmacodynamics of SBT777101 and for exploratory biomarker analysis.

The Sponsor may store samples for up to 15 years after the end of the study to achieve study objectives. Additionally, with subjects' consent, samples may be used for further research by Sponsor or others such as universities or other companies to contribute to the understanding of RA or other diseases, the development of related or new treatments, or research methods.

7.2.6.4.1. Pharmacodynamic Biomarkers

Pharmacodynamic (PD) effects of SBT777101 will be evaluated by measurement of relevant inflammatory cytokines (including but not limited to: IL-1, IL-6, IL-10, IL-15, IL-17, TNF α and interferon-gamma (IFN γ)) and chemokines, as well as measurement of levels of C-reactive protein (CRP) and ACPA pre-dose and after dosing.

7.2.6.4.2. Exploratory Biomarkers

Exploratory biomarkers will include but are not limited to enumeration and phenotyping of CAR T_{reg} cells in peripheral blood by flow cytometry, immunophenotyping of peripheral blood T cell and other immune cell subsets by flow cytometry, and molecular profiling studies using samples collected pre- and post SBT777101 treatment. These studies will inform and enable discovery of potential new biomarkers of response to treatment.

7.2.7. Clinical Assessments

7.2.7.1. Synovitis Assessment

Physical examination and/or ultrasound will be performed to confirm presence of synovitis in the joint considered for synovial biopsy according to local clinical practice. Synovitis of the joint selected for biopsy will also be assessed using these techniques during the study.

7.2.7.2. Efficacy Assessments

ACR and DAS28 response rates will be used to evaluate efficacy responses. Joint count assessments should be performed by the same assessor throughout the study where possible.

The components of these efficacy instruments include evaluation of:

- Swollen and tender joint count (includes assessment of 28 and 66 swollen joints and/or 28 and 68 tender joints)
- Subject's assessment of arthritis pain (using a 100 mm visual analogue scale (VAS))
- Subject's global assessment of arthritis (using a 100 mm VAS)
- Physician's global assessment of arthritis (using a 100 mm VAS)
- Health Assessment Questionnaire-Disability Index (HAQ-DI) to assess subject's physical functioning.

Fatigue will also be measured using the Functional Assessment of Chronic Illness Therapy - Fatigue (FACIT-F) score.

